12.0 Potential Benefits to Subjects and Others

12.1 Potential Benefits to Subjects

Describe the potential benefits that individual subjects may experience from taking part in the research. If there is no direct benefit to subjects, indicate as such. Compensation is not considered a benefit. Compensation should be addressed in section 14.0.

Participants may increase their physical activity and experience increased physiological and psychological health benefits accordingly.

12.2 Potential Benefits to Others

Include benefits to society or others.

Results from this study may lead to new intervention approaches for lifestyle changes.

13.0 Sharing Results with Subjects

Describe whether results (study results or individual subject results, such as results of investigational diagnostic tests, genetic tests, or incidental findings) will be shared with subjects or others (e.g., the subject's primary care physicians) and if so, describe how it will be shared.

Participants will not receive individual results. They may request a copy of any publications summarizing results from the research.

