1.3 Secondary Study Endpoints

State the secondary endpoints to be measured in the study.

1. Total PA Volume: Fitbit Charge 2 HR (step counts) worn from baseline to 3 months
2. MVPA: Actigraph GT3XP-BTLE (bout frequency & duration)
3. Automatic affective evaluations of PA: Single-Category Implicit Association Test in lab
4. Reflective affective judgments of PA: Physical Activity Enjoyment Scale; Behavioral Regulations in Exercise Questionnaire-2+ via self-reports in lab
5. Cardiac reserve; fitness capacity: 3-min step test; predicted VO₂max
6. Cycle ergometer
7. Cardiovascular health: Cardiometabolic panel via phlebotomy (15 mL serum sampling)
8. Macrovascular function: Brachial artery flow-mediated vasodilation
9. Microvascular function: Cutaneous microcirculatory assessment of NO-mediated vasodilation acetylcholine dose-response with/without NO-synthase inhibition (L-NAME)

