3.3 Early Withdrawal of Subjects

3.3.1 Criteria for removal from study

Insert subject withdrawal criteria (e.g., safety reasons, failure of subject to adhere to protocol requirements, subject consent withdrawal, disease progression, etc.).

Research is optional, and participants have the right to withdraw their consent at any time throughout the study. When withdrawing from the study, the participant should let the research team know that he/she wishes to withdraw. Participants may provide the research team with the reason(s) for leaving the study but are not required to provide their reason. Refusal to take part in or withdraw from this study will involve no penalty or loss of benefits one would receive otherwise.

If participants have a recurrence of cancer during the study period and initiate a new round of treatment they will be removed from the study, consistent with the study's exclusion criteria.

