The nurse draws about 30 ml (2 Tbsp) of blood from a vein in the subject's arm. We send the blood to labs for some analyses. If the subject takes thyroid hormone, we draw an extra 3.5 ml (0.2 Tbsp) to check the level of thyroid hormone. Screening tests performed on blood: CBC, Lipid panel, and blood chemistry, Interleukin Panel (IL), folic acid and B12, homocysteine, oxidized LDL, total antioxidant capacity. We do not perform genetic analyses on the blood nor look for presence of disease (e.g. HIV).

Macrovascular Function: Flow Mediated Dilation (FMD)

FMD is an assessment of conduit vessel endothelial function. A blood pressure cuff is placed on the forearm, gel on the upper arm just above the elbow, and a Doppler ultrasound probe on the gel. The ultrasound measures vessel size and blood velocity. After a 3-minute "resting" measurement, we inflate the cuff for 5 minutes to occlude forearm blood flow. After deflating the cuff, we perform a second reading.

Microvascular Function: Microdialysis (MD)

The MD experiment directly quantifies nitric oxide-mediated vasodilation in the microcirculation. Subjects undergo MD at baseline. They repeat MD 3 and 6 months after the baseline experiment.

Preparation for all MD experiments:

Women of childbearing potential undergo a urine pregnancy test.

The participant washes a ventral forearm with antimicrobial soap.

The participant washes a ventral forearm with antimicrobial soap.

Microdialysis probe insertion:

A tight band is placed around the participant's arm to visualize veins.

For each MD site, a pair of pen-marks is made on the arm 2.5 cm (1 inch) apart and away from veins. The tight band is removed. The MD tubing enters and exits the skin at the marks.

The participant's ventral forearm is cleaned with povidone iodine and alcohol, and an ice bag is placed on the arm for 5 minutes to numb the skin. Then a thin needle is inserted into the skin at each entry mark. The needle's tip travels between the layers of skin for 2.5 cm (1 inch) and exits the skin at the matching exit mark. The MD tubing is threaded through the needle, and then the needle is withdrawn leaving the tubing in the skin. Any hyperemia related to the insertion subsides in about 60 minutes.

We place a cuff on the upper arm sans the MD probes to measure BP.

We apply a local skin heater and laser Doppler probe over each MD site.

We measure local skin temperature and skin blood flow (SkBF) throughout the MD experiments.

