7.2.4 Lab Visit 2 (Month 3)

Three months following the baseline visit, participants will be asked to return to the lab to repeat measures taken during the baseline assessment. The researcher will remove the HeartPhone app from the participant's phone. Participants will be set up with an Actigraph accelerometer and given a 1-week wear log to record their activity for one week. Participants will then mail the accelerometer back at the end of the week.

A modification is proposed to include additional questions in the questionnaire pertaining to the acceptability of the Heartphone app. We will also engage in a brief semi-structured interview with the participants at this time to further gauge their experience using the HeartPhone app. The additional questions to be included in the questionnaire and semi-structured interview guide have been uploaded in the Other Attachments section of the Local Site Documents.

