7.2.5 Lab Visit 3 (Month 6)

Participants will then be asked to come back into the lab one final time approximately 6 months following their initial baseline visit. All measures taken at baseline and 3 months will again be taken at 6 months.

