19.2 Recording of Adverse Events

Address the frequency and process for eliciting adverse event information from research subject, e.g., “Research subjects will be routinely questioned about adverse events at study visits.”

In the response, incorporate the following as written:

All adverse events (serious or non-serious) and abnormal test findings observed or reported to study team believed to be associated with the study drug(s) or device(s) will be followed until the event (or its sequelae) or the abnormal test finding resolves or stabilizes at a level acceptable to the investigator.

An abnormal test finding will be classified as an adverse event if one or more of the following criteria are met:

- The test finding is accompanied by clinical symptoms
- The test finding necessitates additional diagnostic evaluation(s) or medical/surgical intervention; including significant additional concomitant drug treatment or other therapy
NOTE: Simply repeating a test finding, in the absence of any of the other listed criteria, does not constitute an adverse event.
- The test finding leads to a change in study drug dosing or discontinuation of subject participation in the clinical research study
- The test finding is considered an adverse event by the investigator.

Research subjects will be routinely questioned about adverse events (e.g., musculoskeletal injuries, cardiovascular events) at study visits and monitored carefully during laboratory procedures.

In the case of untoward events, those lab members present during the event are included in a debriefing and notes of the meeting are taken. The participant involved in an untoward event is interviewed in person or via telephone concerning the event and the responses are included into the notes for that event.

All adverse events (serious or non-serious) and abnormal test findings observed or reported to study team believed to be associated with the study drug(s) or device(s) will be followed until the event (or its sequelae) or the abnormal test finding resolves or stabilizes at a level acceptable to the investigator.

An abnormal test finding will be classified as an adverse event if one or more of the following criteria are met:

- The test finding is accompanied by clinical symptoms
- The test finding necessitates additional diagnostic evaluation(s) or medical/surgical intervention; including significant additional concomitant drug treatment or other therapy

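### Section 13.0 bars return of individual results without exception, although clinical-grade blood tests are run and no visible step tells a participant of a result that needs evaluation

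*Combined protocol and SAP*

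**What the plan says.** The prompt in section 13.0 asks whether individual results, incidental findings among them, will be shared with participants or others such as primary care physicians. The reply is "Participants will not receive individual results", followed only by an offer of publications on request. It contains no exception and does not mention physicians.

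Section 7.2.2 includes a blood draw of about 30 ml among the Lab Visit 1 assessments. It lists "Screening tests performed on blood: CBC, Lipid panel, and blood chemistry", along with research assays such as interleukins and oxidized LDL. It adds: "If the subject takes thyroid hormone, we draw an extra 3.5 ml (0.2 Tbsp) to check the level of thyroid hormone".

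For later visits, section 7.2.4 says that "participants will be asked to return to the lab to repeat measures taken during the baseline assessment", and section 7.2.5 says "All measures taken at baseline and 3 months will again be taken at 6 months". Neither names the blood draw.

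On safety handling, section 19.2 makes an abnormal test finding an adverse event under several criteria, one being: "The test finding necessitates additional diagnostic evaluation(s) or medical/surgical intervention". Section 19.3 requires prompt investigator review of abnormal findings. Section 20.1.2 has adverse events assessed by a licensed medical professional who is an investigator on the study.

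**The concern.** CBC, lipid panel, chemistry and thyroid level are ordinary clinical tests, and any of them can return a value that a clinician would want followed up. The protocol anticipates findings that need work-up (19.2), yet it also says without qualification that participants get no individual results (13.0). If 13.0 is applied as written, a participant with such a result has no stated route to learn of it, and staff must reconcile the two sections case by case. What is at stake is participant safety and clarity for staff, not the trial's inference.

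**Working it through.** The plan states no figure on this point to reproduce. The check sets the sections side by side and then counts the panels.

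**Is there a written step to tell the participant or a physician?**

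- *13.0.* No return of individual results; no exception.
- *7.2.2.* The team says it performs no genetic analysis and does not test for disease, with HIV as its example. That limits which tests are ordered. It does not stop a CBC or chemistry value from being abnormal.
- *19.2, classification.* A finding that requires further diagnosis or treatment becomes an adverse event. This list is not restricted to findings tied to a drug or device, but classification is a recording step and no notification is attached.
- *19.2, follow-up.* Following a finding to resolution applies only where it is thought to be linked to a study drug or device. The test articles in 7.4.1 are the microdialysis agents and their vehicle, used in the 10-person ancillary study, so 30 − 10 = 20 participants receive none. Even if the app counts as a device, the month 0 blood belongs to the same visit at which it is installed, so a month 0 result would not ordinarily qualify.
- *19.2, interview after an untoward event.* This collects the participant's account; it does not convey a result.
- *19.3 and 20.1.2.* Review, causality, seriousness and assessment of adverse events. These are internal steps.
- *16.4.* Monitoring by staff, a defibrillator and emergency calls.
- *10.1 to 10.8.* All marked not applicable.

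No visible section contains the step.

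**How many panels are involved?**

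- Explicit: 30 participants × 1 visit (month 0) = 30.
- Upper limit if the full panel is repeated at months 3 and 6, with full enrollment and no missed visits: 30 × 3 = 90.
- Resting on inference: 90 − 30 = 60.

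The inference is not firm. The repeat wording in 7.2.4 and 7.2.5 is general, and section 1.3 lists only a cardiometabolic panel from 15 mL, against about 30 ml in 7.2.2. It is therefore not stated that CBC and thyroid level are repeated. The month 0 draws are enough for the point.

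These figures count draws, not harm. The documents give no rate of results needing action, so no expected number of affected participants can be derived from them.

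**Can a result still be traced to a person?** Specimens sent to outside laboratories carry codes only (9.1.4). The times stated for destroying the link differ: end of data collection (9.1.1), completion of the study (9.1.1.1), and completion plus publication for the Noll Lab data (9.1.2). Any communication has to happen while a link exists. No assay schedule is given, and 9.1.2 describes freezer storage, so the documents do not show that every result would be available before the earliest of these times.

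**The case against.** The strongest reply is that 13.0 sets a general policy on research results and is not meant to restrain clinicians. Its prompt asks whether results will be shared and, if so, how; a plain no answers it. Safety handling belongs in section 19, where a finding that needs diagnostic evaluation is classified and promptly reviewed. A participant can hardly be evaluated, or withdrawn because of a result, without being contacted, so notification is implied. The consent forms, where such a statement would usually stand, were not available. Nor was the Physician Oversight SOP that 7.4.6.3 cites for the microdialysis agents.

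Much of this stands. It is quite possible that 13.0 means only that results are not routinely returned, and staff may well call someone with an alarming value. But the contact is inferred, and the inference runs against the flat wording of 13.0. If the consent form holds an exception, 13.0 as written contradicts it, and aligning the two is still worthwhile.

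A reader might go further and infer from 3.3.1, which opens "If participants have a recurrence of cancer during the study period", that the protocol expects study blood tests to reveal relapse in leukemia or lymphoma survivors. The text does not support that. It is a withdrawal rule for a recurrence for which new treatment is started, and it says nothing about how the recurrence is found. A reader might also want to put a probability on at least one actionable result among the 30 participants. The documents offer no rate on which to base one.

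**Conclusion.** The point holds as a minor, inexpensive improvement in participant safety. Section 13.0 excludes return of individual results without exception, clinical-grade blood tests are drawn from all 30 participants at month 0, and the review steps in sections 19 and 20 stop short of informing the participant. The size is 30 explicit panels and at most 90, with the frequency of results needing action unknown.

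This rests on two conditions: that the consent forms and the Physician Oversight SOP, neither of them seen, do not already supply the step, and that 13.0 would be applied as worded. It would be too strong to say that the protocol forbids staff from acting on a dangerous result or that participants will be harmed; the documents show only that no notification step is written. Endpoints, sample size and analysis are unaffected.

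**What to change.** Check the consent forms first. If they already contain an exception, carry it into 13.0. If not, add one sentence to 13.0 and align the forms, for example:

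*Any clinical laboratory result (CBC, lipid panel, blood chemistry, thyroid level) that the investigator's review under 19.3, with the licensed medical professional of 20.1.2, judges to need clinical evaluation or intervention will be communicated promptly to the participant and, with the participant's permission, to their physician, while the code link still exists. Research-grade measures, such as flow-mediated dilation, microdialysis, interleukins and oxidized LDL, will not be disclosed.*

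The team should also confirm that the clinical panels are reported before the earliest stated destruction of the code key, the end of data collection in 9.1.1. If assays are batched later, the sentence alone would not achieve prompt communication.

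The cost is one sentence, a check of the consent forms and possibly their revision. No new review role is needed, provided the 19.3 review of abnormal findings covers these panels, as its wording suggests. The downside is that some findings passed on to participants may prove harmless.

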14.0 Subject Stipend (Compensation) and/or Travel Reimbursements

Describe the amount and timing of any subject stipend/payment or travel reimbursement here. If there is no subject stipend/payment or travel reimbursement, indicate as not applicable.

If course credit or extra credit is offered to subjects, describe the amount of credit and the available alternatives. Alternatives should be equal in time and effort to the amount of course or extra credit offered.

If an existing, approved student subject pool will be used to enroll subjects, please indicate as such and indicate that course credit will be given and alternatives will be offered as per the approved subject pool procedures.

Participant compensation is requested and will be allocated separately for the main study ($n = 30$; 3 visits X \$20/visit) and ancillary laboratory study ($n = 10$; 3 visits X \$100/visit). Participants will also keep the Fitbit activity monitor worn throughout the study. In sum, participants in the main study ($n = 30$), will receive \$60 for completing the study. Those in the ancillary study ($n = 10$), will receive an additional \$300 for completing all portions of the ancillary study as well as \$60 for their participation in the main study for a total of \$360).

15.0 Economic Burden to Subjects

15.1 Costs

Describe any costs that subjects may be responsible for because of participation in the research.

Up to 6 megabyte (MB) may be deducted from participants' mobile data plan or charged for the use of the application as a result of study participation (approximately 30 to 60 cents over the course of the entire study). Participants will be responsible for any travel costs related to transportation to and from the lab.

15.2 Compensation for research-related injury

If the research involves more than Minimal Risk to subjects, describe the available compensation in the event of research related injury.

If there is no sponsor agreement that addresses compensation for medical care for research subjects with a research-related injury, include the following text as written - DO NOT ALTER OR DELETE:

It is the policy of the institution to provide neither financial compensation nor free medical treatment for research-related injury. In the event of injury resulting from this research, medical treatment is available but will be provided at the usual charge. Costs for the treatment of research-related injuries will be charged to subjects or their insurance carriers.

For sponsored research studies with a research agreement with the sponsor that addresses compensation for medical care for research-related injuries, include the following text as written - DO NOT ALTER OR DELETE:

It is the policy of the institution to provide neither financial compensation nor free medical treatment for research-related injury. In the event of injury resulting from this research, medical treatment is available but will be provided at the usual charge. Such charges may be paid by the study sponsor as outlined in the research agreement and explained in the consent form.

In the unlikely event a participant becomes injured as a result of participation in this study, medical care is available. It is the policy of the institution to provide neither financial compensation nor free medical treatment for research-related injury. In the event of injury resulting from this research, medical treatment is available but will be provided at the usual charge. Costs for the treatment of research-related injuries will be charged to participants or their insurance carriers.

16.0 Resources Available

16.1 Facilities and locations

Identify and describe the facilities, sites and locations where recruitment and study procedures will be performed.

If research will be conducted outside the United States, describe site-specific regulations or customs affecting the research, and describe the process for obtaining local ethical review. Also, describe the principal investigator's experience conducting research at these locations and familiarity with local culture.

This research will be conducted in the Penn State University at the University Park campus. The lab sessions will be carried out in 17 Rec Hall and in the Noll Laboratory. The Noll laboratory is a 4-floor (35,000 sq. ft.) free-standing building devoted to basic, clinical, and applied physiological research. Biochemistry laboratories are available for sample processing and analyses. Available equipment includes centrifuges, critical care monitors, sonicator, microbalances, laser doppler flowmeters, mini-syringe pumps/ controllers, hospital beds, ECG analysis system, Finipres, refrigerators, pharmaceutical refrigerator, -20 C and -80 C freezers, local skin cooling/ heating systems, blood pressure monitors, metabolic cart, gas sterilization equipment, treadmills, bikes, semi-recumbent cycle ergometer, and autoclave facilities. In addition to ample office and laboratory laptop or desktop computers for research and student use, and a trunk line connection to the University's mainframe computer system. Internal, office and laboratory computers are linked. The laboratory has four PC-based data acquisition systems (DAQ) equipped with Dataq-based DAQ system driven by Windaq software or a PowerLab, DAQ system. A Clinical Research Center (CRC) is contiguous to the Noll Laboratory in the 14,000 sq. ft. Elmore wing. The CRC is readily available for research support.

16.2 Feasibility of recruiting the required number of subjects

Indicate the number of potential subjects to which the study team has access. Indicate the percentage of those potential subjects needed for recruitment.

Based on available data in the Centre County region, the average annual incidence rate per 100,000 people is 108 for breast cancer, 32 for lymphoma, and 20 for leukemia each year. Nationally, the

incidence rate for breast cancer is 124.7, 18.9 for lymphoma and 13.6 for leukemia each year. Based on those annual estimates and the possible age range of participants (18-65) and a diagnosis within the past 15 years, we will need to recruit approximately 0.01% of eligible individuals (based on national estimates) to meet our sample size of 30 cancer survivors.

